The primary outcome measure will be the annualised rate of clinically significant exacerbations (i.e. exacerbations requiring systemic CSs and/or hospitalisation and/or ED visit [see [Section 8.2.2](#)]) measured over the 52-week treatment period. Additional efficacy assessments will include lung function (pre- and post-bronchodilator FEV₁), asthma control (ACQ-5), HRQoL measured with SGRQ, fatigue (PROMIS items), nasal symptoms (SNOT-22 questionnaire), daytime and night-time asthma symptoms (ADSD/ANSD), and daily electronic diary (eDiary) parameters including peak flow, rescue use, daily symptoms and nocturnal awakening due to asthma (see [Section 8.2](#)).

The study will include safety (see [Section 8.3](#) and [Section 8.4](#)) and immunogenicity (see [Section 8.8](#)) assessments to characterise the safety profile of GSK3511294 100 mg SC following repeat dosing. In addition, blood samples will be collected for assessment of PD effects (blood eosinophils) (see [Section 8.7](#)) and PK of GSK3511294 (see [Section 8.5](#)).

After randomisation, all participants will be encouraged to remain in the study and complete all scheduled visits, regardless of whether they receive the second dose of study intervention at Week 26. Participants who experience any of the study intervention

discontinuation conditions (listed in Section 7.1) will not receive another dose of study intervention.

Study visits may be conducted remotely (by a home healthcare professional) or virtually, however, in-person clinic visits are required for the following: pre-screening Visit 0, screening Visit 1, randomisation Visit 2, Visit 3, Visit 10, Visit 11, Exit Visit 17, and WS Visit (if applicable). Participants who are unable to attend their scheduled clinic visits due to COVID-19 restrictions or other unexpected events may complete some visits at home (see Appendix 11). Note: study intervention will only be administered in the clinic (at Week 0 and Week 26 visits).

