6. STUDY INTERVENTION AND CONCOMITANT THERAPY

Study intervention is defined as any investigational intervention(s)/product(s) (IP), marketed product(s), placebo, or medical device(s) intended to be administered to a study participant according to the study protocol.

Study intervention will only be administered in the clinic; hence Visit 2 (Week 0) and Visit 10 (Week 26) are required to be in-clinic visits.

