6.3. Preparation/Handling/Storage/Accountability

- The investigator or designee must confirm appropriate temperature conditions have been maintained during transit for all study intervention received and any discrepancies are reported and resolved before use of the study intervention.
- Only participants enrolled in the study may receive study intervention and only authorised site staff may supply or administer study intervention.
- All study interventions must be stored in a secure, environmentally controlled, and monitored (manual or automated) area in accordance with the labelled storage conditions with access limited to the investigator and authorised site staff.
- The investigator, institution, or the head of the medical institution (where applicable) is responsible for study intervention accountability, reconciliation, and record maintenance (i.e., receipt, reconciliation, and final disposition records).
- Further guidance and information for the final disposition of unused study intervention are provided in the SRM.
- Under normal conditions of handling and administration, study intervention is not expected to pose significant safety risks to site staff. Take adequate precautions to avoid direct eye or skin contact and the generation of aerosols or mists. In the case of unintentional occupational exposure notify the monitor, Medical Monitor and/or GSK study contact.

- A Material Safety Data Sheet (MSDS)/equivalent document describing occupational hazards and recommended handling precautions either will be provided to the investigator, where this is required by local laws, or is available upon request from GSK.

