- Where applicable country and local regulations and infrastructure for home healthcare allow, home healthcare may take place at a location other than the clinical trial site to perform study assessments, which may include collection of blood and urine samples, measurement of vital signs and weight, and preparation and administration of study drug (at the discretion of the investigator). It is the

responsibility of the investigator to inform GSK when this occurs and to document in source notes.

- Remote visits may be performed at the participant's home by qualified study personnel or at a local medical facility, unless the investigator deems that a site visit is necessary.
- Additional unscheduled safety assessments such as routine blood sampling may be performed at the discretion of the investigator including in the participant's home, if deemed necessary. Biological samples may be collected at a different location, other than the study site (e.g., at participant's home) by qualified study personnel or at a local medical facility according to standard operating procedures and applicable regulations (see note). Biological samples should not be collected if they cannot be processed in a timely manner or appropriately stored until the intended use.
- If visits to a site/home are not feasible, then the medical evaluation of the participant's asthma may take place by telemedicine which will use secure video conferences, phone calls, and a web portal and/or mobile application as a way of communicating with and monitoring the participant's progress. GSK will be accountable for working with the vendor to ensure the site has the required equipment, training and support for this model and should be notified as soon as possible by the investigator that the service is required.

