- The study investigator is responsible for ensuring that the identification, management, and reporting of AEs and SAEs are completed in accordance with the protocol and applicable regulations. AEs are first reported by participants to the investigator/study team or may be identified by the study team during interactions with the participants via telemedicine encounters. In addition, mobile nurses may identify AEs as well and report them to the investigator for evaluation. Additionally, AEs may be identified from lab reports, imaging or ECG reports, and other records. As determined by the investigator, the appropriate medical intervention, therapeutic intervention, and/or support measures are instituted, as necessary.
- The participant should be informed of the plan and any potential risks associated with the virtual medium and sign a revised Informed Consent Form if required. IRB/Ethics committee should be informed and/or approve of this change in approach and the process documented in study files.
- The revised schedule of study activities is provided in [Table 6](#).

Note: If the investigator wishes to conduct a trial visit at a location that has not been previously assessed by GSK, it is the investigator's responsibility to identify an adequate alternate location and to notify GSK of the alternate location. The investigator should ensure that this alternate location meets ICH GCP requirements, is well-equipped to perform study procedures and covered by an adequate insurance. Furthermore, the investigator should have sufficient oversight to ensure that the staff at the alternate location are trained to perform study procedures. Refer to and follow most recent local guidance and regulations if available or refer to FDA or EMA guidance available at time.

Study Intervention:

- If despite best efforts it is not possible to administer the dose of study intervention as defined in the protocol (see Section 6 Study Intervention and Concomitant Therapy), a maximum dose interval of 28 weeks may be used.
- In-clinic visits are required for administration of the study intervention (Week 0 and Week 26).
- In some cases, trial participants who no longer have access to study intervention or the investigational site may need additional safety monitoring (e.g., on withdrawal of an active investigational treatment).

Data Management/Monitoring:

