- White boxes represent activities/assessments that are to be done during visits to the clinical study centre (pre-screening Visit 0, screening Visit 1, randomisation Visit 2, Visit 3, Visit 10, Visit 11, Exit Visit 17, and WS Visit if applicable).
- Grey boxes represent activities/assessments during study visits (Visits 4-9, Visits 12-16, and the FU Visit) that may be conducted by a home healthcare professional, where applicable country and local regulations and infrastructure allow (at the discretion of the investigator, based on safety and tolerability).
- The FU Visit may be conducted as a remote/home visit or as a phone call.
- During home visits, the scheduled collection of samples for laboratory and other assessments may be performed by a home healthcare professional.

Table 6 Schedule of Activities (SoA) Indicating Assessments that may be Conducted Outside of a Clinical Study Site

Protocol Activity	Pre-Screening	Screening/Run-in	Intervention Period and Exit Visit (visit window is ±7 days)																	Follow-up/Withdraw (±7 days)		Notes
			Visit	V0 ^a	Visit 1 ^a	V2 ^b R*	V3	V4	V5	V6	V7	V8	V9	V10	V11	V12	V13	V14	V15	V16	Exit V17	
Study Week	-8 to -6	-6 to -1	0	2	4	8	12	16	20	24	26	28	32	36	40	44	48	52	26 or 52	56	R* =Randomisation WS=Withdraw from study visit (see footnote c) FU=Follow-up visit/call (only required for participants not entering OLE study)	
Study Day	-56 to -42	-42 to -7	1	14	28	56	84	112	140	168	182	196	224	252	280	308	336	364		392		
General Eligibility Assessments																						
Informed consent ^a	X	(X)																				Conduct at Visit 1 if not completed at Visit 0; See footnote a.
Genetic sample informed consent ^d	X	(X)																				Conduct at Visit 1 if not completed at Visit 0; See footnote d.
Demography data collection	X	(X)																				Conduct at Visit 1 if not completed at Visit 0; All females must be assessed at Visit 1 to determine childbearing potential.
Inclusion/Exclusion criteria	X	X																				
Historical blood eosinophil count		X																				See footnote e.
Medical history		X																				Include cardiovascular (CV), CV risk factors, asthma, exacerbations, vasculitis, allergies and anaphylaxis.
Smoking status		X																				

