Clinical Chemistry		X	X		X	X	X		X		X	X			X		X	X	X		Include liver chemistry.	
Pregnancy Test (WOCBP only)		X	X		X	X	X	X	X	X	X		X	X	X	X	X	X	X	X	X	Serum pregnancy test should be done at screening Visit 1 and Exit Visit/Withdraw from study visit; urine pregnancy tests should be done for all other assessments; WOCBP=Women of childbearing potential; See Section 8.3.5 for additional information.
Urinalysis		X	(X)								X							X	X		Conduct at Visit 2 if not completed at Visit 1. Note: dipstick, send for analysis if abnormality is identified by dipstick	
Anti-MPO antibody, anti-PR3 antibody, ANA, and anti-dsDNA antibody			X																		ANA=antinuclear antibodies; MPO=myeloperoxidase; PR3=proteinase 3. Collected baseline sample will be stored and may be tested if necessary (see Section 7.5).	
Complement C3 and C4			X				X				X				X			X	X			
PK sample			X	X	X	X	X		X		X	X	X		X			X	X		For dosing days (Week 0 and Week 26), obtain sample prior to dosing.	
Immunogenicity sample			X	X	X	X	X				X	X	X	X	X			X	X			

Protocol Activity	Pre-Screening	Screening/Run-in	Intervention Period and Exit Visit (visit window is ±7 days)																	Follow-up/Withdraw (±7 days)		Notes
			Visit	V0 ^a	Visit 1 ^a	V2 ^b R*	V3	V4	V5	V6	V7	V8	V9	V10	V11	V12	V13	V14	V15	V16	Exit V17	
Study Week	-8 to -6	-6 to -1	0	2	4	8	12	16	20	24	26	28	32	36	40	44	48	52	26 or 52	56	R* =Randomisation WS=Withdraw from study visit (see footnote c) FU=Follow-up visit/call (only required for participants not entering OLE study)	
Study Day	-56 to -42	-42 to -7	1	14	28	56	84	112	140	168	182	196	224	252	280	308	336	364		392		
Blood biomarker sample			X				X				X				X			X			Sample will be stored and may be analysed for exploratory biomarkers (see Section 8.7.3)	
Genetics sample			←===== The genetics sample can be collected at Visit 2 or any visit after =====→																			See footnote d.
Study intervention																						
Administer study intervention			X									X									Study intervention will only be administered in the clinic. Any scheduled assessments or sample draws should be performed beforehand. Monitor participant for at least 2h after administration (see Section 6.5).	
eCRF/worksheets/other																						
Dispense Rescue medication		X	X	X	X	X	X	X	X	X	X	X	X	X	X	X	X					
Register Visit in the IRT system		X	X								X								X		IRT=interactive response technology	

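### One bullet in the COVID-19 appendix lets home healthcare give study drug, against the clinic-only dosing rule stated everywhere else in the protocol

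*Protocol*

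**What the plan says.** Appendix 11 sets out measures for sites affected by COVID-19. Under its heading on protocol-defined procedures and visits, the first bullet allows home healthcare away from the trial site where local rules and infrastructure permit. The tasks listed are blood and urine collection, vital signs, weight, and "preparation and administration of study drug (at the discretion of the investigator"). The investigator must tell the sponsor when this happens and record it in source notes.

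Later in the same appendix, the text on study intervention says: "In-clinic visits are required for administration of the study intervention (Week 0 and Week 26"). For a dose that cannot be given as planned, the relief offered is that "a maximum dose interval of 28 weeks may be used".

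Section 4.1 allows some home visits under Appendix 11 and then immediately adds: "Note: study intervention will only be administered in the clinic (at Week 0 and Week 26 visits").

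**The concern.** The protocol gives two incompatible answers on where a dose may be given under pandemic restrictions. A site that cannot bring a participant in for Week 26 would turn to Appendix 11, because its opening names difficulty in giving study intervention as one of the problems it addresses. The first procedural bullet such a site meets gives discretion to dose at home and asks for notification, not prior approval. There is also an incentive to give the dose, because Section 6.7 makes both doses a condition of entry to the open-label extension.

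Two safeguards are at stake:

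- **Observation after the dose.** Section 2.3.1 lists at least 2 hours of in-clinic monitoring, at randomisation and at Week 26, as a mitigation for allergic reactions including anaphylaxis. Section 6.5 adds trained staff on site. Week 26 is re-exposure to a long-acting antibody: Section 6.8 gives a half-life of about 41 days and says there is no known antidote.
- **ECG before the dose.** Section 1.3 requires the ECG to be done and assessed pre-dose. Under Section 7.1.2 the machine read at Visit 10 is the value used for the QTc stopping criteria. The tasks named in the home-healthcare bullet do not include an ECG.

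**Working it through.** No figure in the plan needs reproducing. The check sets the statements on place of dosing side by side.

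| Place in the protocol | Where dosing may occur |
|---|---|
| Appendix 11, first bullet on procedures and visits | Off site, at the investigator's discretion |
| Section 1.3, dosing row | Clinic only |
| Section 4.1, note after the reference to Appendix 11 | Clinic only |
| Section 6 | "Study intervention will only be administered in the clinic"; Visits 2 and 10 must therefore be in clinic |
| Section 6.4.1 | In the clinic at Visits 2 and 10 |
| Section 6.5 | Study site, with at least 2 hours of in-clinic monitoring |
| Appendix 11, study intervention text | In-clinic visits required |
| Appendix 11, list of on-site visits | Visits 2 and 10 are on the list |
| Appendix 11, Table 6, dosing row | "Study intervention will only be administered in the clinic. Any scheduled assessments or sample draws should be performed beforehand" |

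**Could the bullet be a deliberate exception?** Three points say no.

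1. Section 4.1 keeps the clinic-only rule in the very place where it allows COVID-19 home visits.
2. Appendix 11 deals with missed dosing under its own heading. It offers a longer interval and then requires the clinic.
3. The appendix names the visits open to home healthcare: "Grey boxes represent activities/assessments during study visits (Visits 4-9, Visits 12-16, and the FU Visit) that may be conducted by a home healthcare professional". Visits 4–9 are 6, Visits 12–16 are 5 and follow-up is 1, so 6 + 5 + 1 = 12 visits. The dosing visits are 2 and 10, and neither is among the 12.

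**Could study drug here mean rescue medication?** Not sensibly. Section 6.9.3 has albuterol/salbutamol dispensed as an inhaler for the participant's own use, so a home nurse would have nothing to prepare or administer.

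**Which doses are exposed?** The Week 0 dose follows in-person randomisation at Visit 2, so in practice only Week 26 is open. The ceiling is the planned sample: 250 + 125 = 375 doses.

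**How much relief does the permitted fallback give?** An interval of 28 weeks is 28 − 26 = 2 weeks past the nominal visit. With the ±7-day visit window ending at Week 27, it is 28 − 27 = 1 week past the window. A site that cannot see the participant within that time has a reason to use the bullet.

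**The case against.** The strongest reply is that the protocol settles the matter itself. The dedicated dosing text in Appendix 11, its visit list and Table 6 all require the clinic, and the disputed words end a generic list of what home healthcare might cover. A careful site would follow the specific rule.

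Other controls also stand in the way. The bullet depends on local regulation and infrastructure. The sponsor must be informed. Visit 10 is registered in the IRT (Section 8.1.1). Study intervention is kept in secure storage with limited access (Section 6.3). An alternate location not previously assessed by the sponsor must be notified and adequately equipped and staffed. Nothing in the bullet expressly waives the 2-hour observation or the pre-dose ECG.

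Much of this stands as a reason to expect few home doses, and the 375 figure is only a ceiling. It is also fair that Section 6.3, under which "only authorised site staff may supply or administer study intervention", governs who may give the dose, not where. A delegated home nurse might count as authorised, so that section is weak evidence on location.

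The reply does not remove the contradiction. The bullet is current, operative text that names drug administration and grants discretion. Its notification duty does not stop the dose being given. In-clinic observation cannot be carried out at home, so a site relying on the bullet would depart from Section 6.5 while believing it had permission. Site training or the study reference manual may already clarify the point, but the documents do not show this.

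**Conclusion.** The concern holds. One bullet permits off-site dosing, while the other statements on place of dosing, including those in the same appendix, require the clinic or study site. The sponsor's intent is evidently clinic-only dosing, so the bullet is wrong as written and should be corrected. It bears on a stated anaphylaxis mitigation and a pre-dose stopping check, which makes it more than an editorial slip.

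The exposure is at most the 375 planned Week 26 doses. That ceiling assumes that every randomised participant reaches Week 26 and is dosed at home, which is unrealistic. The documents give no basis for a better estimate. Power, type I error, the estimands and the analysis models are unaffected.

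**What to change.** In the first procedural bullet of Appendix 11, delete the words on preparing and administering study drug, so that the task list ends at vital signs and weight. Add a sentence there saying that dosing stays in the clinic with at least 2 hours of monitoring under Section 6.5, and that the only pandemic relief is a dose interval of up to 28 weeks.

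Send sites a clarification now and correct the text at the next amendment, with whatever ethics committee approval Section 10.1.1 requires. If Week 26 dosing has already taken place, check whether any dose was given off site. Section 6.5 names only date and time among the dosing details for the CRF, so this check may need the source notes that the bullet asks for.

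The cost is one line of wording, a memo and, where needed, a short records check. Design, sample size and analysis do not change.

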10.12. Appendix 12: Country-specific requirements

No country-specific requirements exist.

10.13. Appendix 13: Abbreviations and Trademarks**Abbreviations**

ACQ	Asthma Control Questionnaire
ADA	Anti-drug antibody
ADE	Adverse device events
ADSD	Asthma Daily Symptom Diary
AE	Adverse event
ALT	Alanine transaminase
ANA	Antinuclear antibodies
ANCA	Anti-neutrophil cytoplasmic antibody
ANSD	Asthma Nightly Symptom Diary
Anti-HBc	Hepatitis B core antibody
Anti-IL-5	Anti-Interleukin-5
Anti-IL-5R	Anti-Interleukin-5 receptor
AST	Aspartate aminotransferase
BiPAP	Bilevel positive airway pressure
BP	Blood pressure
BUN	Blood urea nitrogen
CI	Confidence interval
CIOMS	Council for International Organizations of Medical Sciences
cm	Centimetre
CONSORT	Consolidated Standards of Reporting Trials
COVID-19	Coronavirus disease 2019
CPAP	Continuous positive airway pressure
CPK	Creatine phosphokinase
CRF	Case report form
CS	Corticosteroid
CSR	Clinical study report
CTFG	Clinical Trial Facilitation Group
CV	Cardiovascular
DNA	Deoxyribonucleic acid
ECG	Electrocardiogram
eCRF	Electronic case report form
ED	Emergency department
eDiary	Electronic diary
EDTA	Ethylenediaminetetraacetic acid or disodium edetate
EGPA	Eosinophilic granulomatosis with polyangiitis
FAAN	Food Allergy and Anaphylaxis Network
FAS	Full Analysis Set
FEV ₁	Forced expiratory volume in 1 second
FP	Fluticasone propionate
FSH	Follicle stimulating hormone
FTIH	First Time in Humans

FVC	Forced vital capacity
g	Grams
GCP	Good Clinical Practice
GCSP	Global Clinical Safety and Pharmacovigilance
GGT	Gamma glutamyl transferase
GINA	Global Initiative for Asthma
GLDH	Glutamate dehydrogenase
GSK	GlaxoSmithKline
h	Hours
HBc	Hepatitis B core
HBsAg	Hepatitis B surface antigen
HFA	Hydrofluoroalkane product
HIV	Human immunodeficiency virus
HRQoL	Health-related quality of life
HRT	Hormone replacement therapy
IB	Investigator's Brochure
ICF	Informed consent form
ICH	International Council on Harmonization of Technical Requirements for Registration of Pharmaceuticals for Human Use
ICS	Inhaled corticosteroid
IDMC	Independent data monitoring committee
IEC	Independent Ethics Committee
IFU	Instruction for use
Ig	Immunoglobulin
IL-5	Interleukin-5
IL-5R	Interleukin-5 receptor
IM	Intramuscular
IMP	Investigational medicinal product
INR	International normalised ratio
IP	Investigational Product
IRB	Institutional Review Board
IRT	Interactive response technology
IUD	Intrauterine device
IUS	Intrauterine hormone-releasing system
IV	Intravenous
kg	kilogram
L	Litre
LA	Long-acting
LABA	Long-acting β -agonist
LAM	Lactational amenorrhea method
LAMA	Long-acting muscarinic antagonist
LDH	Lactate dehydrogenase
LTRA	Leukotriene receptor antagonist
mAb	Monoclonal antibody
MAR	Missing at random

mcg (μ g)	Microgram
MDI	Metered dose inhaler
MedDRA	Medical Dictionary for Regulatory Activities
mg	Milligrams
mL	Millilitres
mm Hg	Millimetre of mercury
mol	Mole
MPO	myeloperoxidase
MSDS	Material Safety Data Sheet
msec	Milliseconds
NAb	Neutralising antibody
NHANES	National Health and Nutrition Examination Survey
NHLBI	National Heart, Lung, and Blood Institute
NIAID	National Institute of Allergy and Infectious Disease
NIH	National Institutes of Health
NIMP	Non-investigational medicinal product
OCS	Oral corticosteroid
OLE	Open-label extension
PC ₂₀	Provocative concentration causing a 20% fall in FEV ₁
PCR	Polymerase chain reaction
PD	Pharmacodynamics
PD ₂₀	Provocative dose that decreases FEV ₁ by 20%
PEF	Peak expiratory flow
PFS	Pre-filled safety syringe
PGI-C	Patient Global Impression of Change
PGI-S	Patient Global Impression of Severity
PK	Pharmacokinetics
PR3	Proteinase 3
PRO	Patient-reported outcomes
PROMIS	Patient-reported outcomes measurement information system
QTcF	QTc corrected by Fridericia's formula
QTL	Quality tolerance limits
R&D	Research and Development
RBC	Red blood cell
RNA	Ribonucleic acid
SABA	Short-acting β -agonist
SADE	Serious adverse device event
SAE	Serious Adverse Event
SAP	Statistical analysis plan
SC	Subcutaneous
SDAC	Statistical data analysis centre
SGOT	Serum glutamic oxaloacetic transaminase
SGPT	Serum glutamic pyruvic transaminase
SGRQ	St. George's Respiratory Questionnaire
SNOT	Sino-nasal Outcomes Test

SoA	Schedule of assessments
SoC	Standard of care
SOC	System organ class
SRM	Study Reference Manual
SRT	Safety review team
SUSAR	Suspected unexpected serious adverse reaction
UACR	Urinary albumin-creatinine ratio
UK	United Kingdom
ULN	Upper Limit of Normal
w/v	Weight/volume
WBC	White blood cell
WOCBP	Women of childbearing potential
WONCBP	Women of non-childbearing potential
µL	Microlitre

Trademark Information

Trademarks of the GlaxoSmithKline group of companies
NUCALA

Trademarks not owned by the GlaxoSmithKline group of companies
CINQAERO
CINQAIR
DUPIXENT
FASENRA
MedDRA
SAS
XOLAIR

